# Literacy (V1)

 Patients' literacy (Using the Rapid Estimate of Adult Literacy in Medicine - REALM-R), Bass (2003): collected by a dental nurse using a laminated sheet of the 8 REALM medical words (including 3 practice words, with the American spelling of anemia substituted for the English spelling anaemia).

Dental visiting and previous dental experiences (V1). Four items were taken from the Adult Dental Health Survey, 2009 (Health and Social Care Information Centre, 2011).

- In general do you go to the dentist for: a regular check-up/an occasional checkup/only when having trouble with my teeth/dentures?
- How many times have you been to the dentist in the last five years purely for a checkup?
- We would like to know about the types of dental care/treatment that you have received from dentists over the course of your whole life. This includes any care or treatment you may have had as a child (Have you ever had fillings/teeth extracted (taken out)/a dental bridge or a tooth crowned/a root canal treatment/a scale and polish?)
- We included an additional question on pain experience: Have you ever experienced dental pain bad enough to make you go to the dentist (tick all that apply): 1=currently in pain, 2=In the last 6 months, 3=6 months to 2 years ago, 4=more than 2 years ago, 5=never).
- Number of failed appointments in the course of the study (from recruitment log records)

Dental Anxiety (MDAS): (V1). The Modified Dental Anxiety Scale (Humphris, et al, 1995) consists of 5 questions relating to how the patient would feel about various aspects of dental treatment if it were to happen tomorrow. For each item there is a 5 category rating scale, ranging from 'not anxious' to 'extremely anxious'.

Self-assessed oral health: (V1, V2, V3, F1, F2) using one item and a 5 point Likert scale: *Would you say your dental health (mouth, teeth and/or dentures) is*: 1=very good, 2=good, 3=fair, 4=poor, 5=very poor was derived from the Adult Dental Health Survey, 2009 (Health and Social Care Information Centre, 2011).

b) Dentists' characteristics collected at V1

Patient-Clinician communication (Communication Assessment Tool, CAT). This 15 item tool is designed to test the interpersonal and communication skills of clinicians (Makoul, Krupat and Chang, 2007). It has been applied in a range of settings including dentistry (Waylen, Makoul and Albeyatti, 2015), where 'doctor' is replaced by 'dentist'. A five point Likert scale is used (1=poor, 2=fair, 3=good, 4=very good, 5=excellent).

Individual clinician code for the appointment (V1, V2, V3)

## 2. Valuation data

# a) Willingness-to-Pay (WTP) - collected at V1

The primary outcome in Phase 2 is the patient valuation of different forms of oral health/risk information. Contingent valuation (in the form of WTP) has been chosen as our measure of value. The principal alternative to this valuation method would be a utility based measure, however no existing oral health related quality of life tools have been successfully mapped to utility scores (Brennan and Spencer, 2006) and direct utility measures (such as standard gamble or time trade off) are unlikely to be sensitive enough to detect the small changes in utility likely to be observed in oral health (Vernazza et al., 2012).

Another alternative to WTP would be discrete choice experiments (DCE), from which WTP can be derived. However, one of the strengths of a DCE is the ability to incorporate and study a number of attributes defining the studied "good" and in this case only 2 attributes are of interest; the presentation of the information and the value (WTP). A DCE would therefore be over-complicated both from a research design and management point of view, and from a participant point of view. The remaining technique, WTP, has been recommended as the most appropriate valuation tool for oral health (Birch and Ismail, 2002; Vernazza et al., 2012).

# b) Cost data:

Cost data will be gathered both prospectively during Phase 2 and using existing routine data sources. Costs will be measured from an NHS perspective and will be calculated, where necessary, using a micro-costing approach. One-off costs such as training and non-consumable equipment will be priced directly. For the remaining costs, for a subsample of 10 participants in each practice (40 participants in total) all costs incurred will be recorded. This will include recording of all consumables used and the time spent recording and delivering the oral health risk status. Interviews with relevant staff at the practice (principal dentist or practice manager) will be used to identify overhead and staff costs. As any behaviour change resulting from the risk information systems to be studied may influence future oral health interventions required, it will be necessary to cost these likely interventions too. These will be costed using existing data including published estimates of costs from other research and national fees and tariffs (e.g. NHS (Dental Charges) Amendment Regulations 2008).

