Following this, patient interviews will take place away from the surgery itself to examine how patients interpret the information given during dental appointments and discuss the alternative forms of information giving the patient would want, need or prefer to receive. Discussion with these patients will involve their thoughts on paying for NHS care, or being exempt from charges, as well as any thoughts they have on changes in NHS dentistry involving a traffic light system of rating patients' risk and need (one of the messages they may receive from consultations, may be that without taking the appropriate action, they won't receive future treatments). This provides the background against which patients' readings of the information they receive will be set, and is highly relevant to studying how they orient to, interpret and act on that information. Where possible all interviews and some of the surgery conversations between the dental team members and the patients relating to information given at the check-up, will be audio-taped and transcribed for analysis.

We will purposively sample to include different adult groups and explore whether differences exist e.g. by age and socio-economic groups. We will explore barriers to healthy oral self-care, and the gains which are perceived to be possible through improvements in their oral health behaviour; looking to identify 'segments', particularly within the population of people at high/medium risk of oral disease, - groups with similar characteristics in terms of identity, lifestyle, opinions, beliefs and behaviours. We anticipate conducting in-depth one-to-one

interviews with patients, although the actual number itself will be guided by the qualitative research principle of data saturation – may be a few more or a few less depending on emergent findings (Spencer et al, 2003).

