## Demographic characteristics

- Socio-economic status measured by area classification: Postcode allocated to IMD quintile
- Whether the patient is exempt from dental charges or not.
- Gender: Male, Female
- Age: in years
- Education: The highest level of education given in 5 categories 1= GCSE or NVQ level 1 or similar, to 5= postgraduate degree.
- Employment status: 1=employed or self-employed full-time, 2=employed or selfemployed part-time, 3=unemployed at the moment, 4= full-time education
- Household Income (before deductions e.g. income tax): according to 9 categories given as weekly or yearly amounts, ranging from 1= £0 to 9= over £52,000 per year

Measures of education and income will be according to the Office for National Statistics (2015) standard ways of categorising households according to demographics.

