## The cost-benefit framework analysis

The valuation data will be most meaningful if compared to costs. Although a cost-benefit analysis would be the ideal way of combining costs and benefits in a meaningful way, a robust cost benefit analysis of oral health risk information would entail modelling changes in disease levels resulting from behaviour change linked to the information given. In turn, it would be important to understand the lifetime (or certainly long term) consequences in terms of costs and benefits of changing disease levels. This would result in a hugely complex model, for which we have very little (and in many areas, no) evidence or data. Such a robust full scale cost-benefit analysis is therefore impossible not possible. We therefore propose to undertake a more limited outline cost-benefit framework analysis.

Thus WTP data will be combined with a cost-benefit framework analysis. The principal outcome of any such analysis would be net benefit or cost in monetary terms (i.e. £). Given that cost-benefit analysis expresses both costs and benefits in commensurate units the decision rule for cost-benefit analysis is therefore relatively simple. If the benefits (measured in £ via WTP) exceed the costs (also measured in £) this represents a gain in welfare and the strategy deemed worthwhile (Drummond et al., 1997). The level of complexity of this analysis will depend on the data available in the literature concerning longer term effects of

risk information and oral health behaviour change on oral health. The cost-benefit framework analysis will also give an indication of the likely effect of any sustained behaviour change. Data from the endpoint of the study (12 months) will be used to illustrate the effect of the behaviour change resulting for the different interventions at this time point. Results will be presented as incremental net benefits (net benefits = mean WTP – mean cost of intervention).

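### The only tariff named for costing future dental treatment is a schedule of patient charges, which does not measure cost from the stated NHS perspective

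*Protocol*

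**What the plan says.** Under Measures, section 2 b) Cost data, the protocol sets the viewpoint: "Costs will be measured from an NHS perspective and will be calculated, where necessary, using a micro-costing approach". One-off items such as training and equipment are priced directly. Other delivery costs come from recording consumables and time for 10 participants per practice (40 in all) and from interviews with practice staff.

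The same section then turns to later treatment that behaviour change might alter, and says "it will be necessary to cost these likely interventions too". For the source it says "These will be costed using existing data including published estimates of costs from other research and national fees and tariffs", and gives one example of a tariff, the 2008 Dental Charges Amendment Regulations: "national fees and tariffs (e.g. NHS (Dental Charges) Amendment Regulations 2008".

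Three other places show how the protocol understands dental charges. The ethnographic study will ask patients for "their thoughts on paying for NHS care, or being exempt from charges". The list of demographic characteristics includes "Whether the patient is exempt from dental charges or not". The Visit 1 procedures have the dentist or nurse record exemption status after the check-up.

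The cost-benefit framework section defines the result as "net benefits = mean WTP – mean cost of intervention". It rules out a full model of long-term disease consequences and says that 12-month data will be used to illustrate the effect of behaviour change. Objective 7 says that the analysis should also explore what the three methods mean financially for NHS dentistry.

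**The concern.** The perspective and the example source sit in one paragraph and do not fit together. Under an NHS perspective, the cost of a treatment is what the NHS spends to provide it. A charge paid by the patient is money coming in, which offsets part of that spending. For an exempt patient nothing comes in, yet the care still has to be paid for. A schedule of charges therefore measures a different quantity from the one the paragraph asks for.

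This is something the protocol states, not a detail it leaves to a later plan. Future treatment is the route by which a change in self-care would alter NHS spending, so its unit costs bear directly on Objective 7. An analyst who followed the example would report, as a consequence for the NHS, a figure that describes what patients are asked to pay.

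**Working it through.** The protocol states no figure to reproduce on this point. The check is a comparison of the relevant sections, followed by two short pieces of arithmetic.

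**1. Perspective against source.**
- Required quantity: "Costs will be measured from an NHS perspective" (Cost data).
- Sources offered for future treatment: published cost estimates, and national fees and tariffs, with the charges regulations as the single example (Cost data).
- Nature of a charge: paid by patients or waived (ethnographic study, Visit 1 procedures, demographic characteristics).

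On the protocol's own description, the example does not measure the required quantity.

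**2. Can the error be sized?** For one course of treatment, let C be the NHS cost of provision, F the patient charge and e the share of patients exempt.
- NHS cost before recovered charges: C. Using F instead gives an error of F − C.
- NHS cost after recovered charges: C − (1 − e)F. Using F instead gives an error of F − [C − (1 − e)F] = (2 − e)F − C.
- For an exempt patient the charge collected is 0 and the NHS cost is C, so costing by charges collected would miss all of C.

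The protocol gives none of C, F or e. The size of the error cannot be computed. Against cost net of recovered charges, even its direction is undetermined, because (2 − e)F − C can take either sign.

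**3. Does the error reach net benefit?** The formula subtracts the mean cost of the intervention. The delivery costs of the three information methods come from direct pricing, micro-costing and staff interviews, none of which uses the charges regulations. The Cost data section says that future interventions must be costed. The cost-benefit section does not say whether those costs enter the formula or are shown beside it. If they stay outside, net benefit is untouched and only the account of NHS financial implications is affected.

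**4. Price level (side point).** The named regulations date from 2008. The protocol cites web pages accessed on 14.8.15, and WTP is elicited at Visit 1 of Phase 2, so a gap of 7 to 9 years (2008 to 2015–2017) is a reasonable assumption. No inflation rate is given, so annual growth g is also assumed. The understatement relative to survey-year prices over y years is 1 − (1 + g)^−y:
- g = 2%, y = 7: 1 − 1/1.149 = 0.129
- g = 3%, y = 7: 1 − 1/1.230 = 0.187
- lowest case, g = 1%, y = 7: 0.067
- highest case, g = 4%, y = 9: 0.297

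This applies only if 2008 values were used without uprating, and only to future-treatment costs drawn from that source.

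**The case against.** The strongest reply is that one parenthesis is being made to carry too much. The regulations are introduced as an example, published cost estimates are listed first, and the wording leaves the list open. The stated NHS perspective could be taken to govern which source is chosen. A reader might infer that all future treatment will be costed at 2008 patient charges; the text does not commit the analysts to that.

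A reader might also infer that net benefit is mis-measured and could change sign. The documents do not support this either. The formula uses the cost of the intervention, which is micro-costed, and nothing says that future treatment costs are added to it.

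Nor does the protocol state that costs and WTP are in different price years. It gives no price year for either and does not exclude uprating. Fixing a price year is commonly left to an analysis plan, so its absence alone is not a fault.

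All three replies stand, and they limit the point. They do not remove it: the one tariff the protocol chose to name measures a patient payment, in a paragraph that asks for NHS cost.

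**Conclusion.** The point holds in a limited form. The protocol offers a schedule of patient charges as its only named tariff for costing future treatment from an NHS perspective. Any figure taken from it would be wrong for that perspective and for the analysis of financial implications for NHS dentistry. This rests on the protocol's own description of charges as paid by patients unless exempt.

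The size of that error is unknown and cannot be derived from the documents. Its effect on net benefit is conditional on future treatment costs being included, which the protocol leaves open. The 13–19% price effect is an illustration resting on assumed growth of 2–3% a year, a seven-year gap and no uprating; it is a secondary matter.

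The primary outcome, the comparison of WTP between forms of information, is unaffected, as are the micro-costed delivery costs. This is a correction to a secondary economic analysis.

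**What to change.** In the Cost data section, replace the charges regulations as the example source with unit costs that reflect what the NHS pays to provide the care. Where patient charges are used at all, enter them only as an offset to that cost, set to nil for exempt patients; exemption status is already collected at Visit 1. State that these unit costs will be at prices matching the year of the WTP survey.

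In the cost-benefit framework section, say whether future treatment costs enter the net benefit or are reported separately.

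The cost is a few sentences of rewording and the work of finding a different published unit-cost source. No new patient data are needed, and the sample size and primary analysis do not change.

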# 3. Oral health behaviours - collected at V1, V2, V3, F1, F2

There is no generally recognised measure of oral health behaviour, with individual studies using measures suited to their research questions and population characteristics. We therefore derived our set of measures for a number of sources.

- a) Questions on diet: were adapted from the National Diet and Nutrition Survey (Walker et al, 2000): 'How often, on average do you eat or drink these things?' (with response in a seven point scale from more than once a day to never); and the Adult Dental Health Survey, 2009 (Health and Social Care Information Centre, 2011): 'Do you usually have sugar (not artificial sweetener) in hot drinks like tea and coffee?'.
- b) One question on oral hygiene behaviour was taken from the Adult Dental Health Survey, 2009 (Health and Social Care Information Centre, 2011): *How often do you brush your teeth nowadays?*, with responses 1=More than twice a day, 2=Twice a

day, 3=Once a day, 4=Less than once a day, 5=Never. This was supplemented with two items adapted from the Index of Oral Hygiene Behaviour (Buunk-Werkhoven et al, 2011): '*How long do you clean your teeth for nowadays*? (with responses 1=longer than 3 minutes, 2= 3 minutes, 3= 2 minutes, 4= 1minute, 5= shorter than 1 minute), and '*How often do you do interdental cleaning*? (e.g. with floss, interdental *brushes, tooth sticks etc*).' with responses 1=At least once a day, 2=At least twice a week, 3=Weekly, 4=Monthly, 5=Never.

- c) Questions on tobacco use were derived from the World Health Organisation (2011) Global Tobacco Surveillance system.
- 4. Intention to Change Behaviour collected at V1

We will assess intentions to change target behaviours using a stem question: 'Before my next appointment I intend to..' using a five point Likert scale 1= Absolutely disagree to 5 = Absolutely agree.

- 5. Risk perception and behaviour change mediators collected at V1, V2 (perceived susceptibility to risk)
  - a) The approach: the Extended Parallel Process Model (EPPM)

Whilst the focus of the study is valuation of information, a secondary aim is to investigate whether patients' information valuation is linked to their intention to change behaviour and any actual behaviour change.

Motivation to change behaviour is stimulated by: awareness that current behaviours involve a risk of negative health or social outcomes and that the risk may be avoided or attenuated by behavioural change (Weinstein and Sandman, 1993), together with an awareness that an individual possesses the capacity to make those changes. Recent work suggests that risk is experienced in emotional terms (Lowenstein, et al. 2001; Weinstein et al 2007), and that measures that access these emotions often provide better prediction of behaviour than likelihood and severity ratings of risk (Weinstein, et al., 2007). We will therefore use the Extended Parallel Process Model (EPPM) as a basis for collection of behaviour change data (Figure 2) since it incorporates both cognitive and emotional variables related to behaviour change (Witte, 1992; 1994; 1996). The EPPM takes a dual process approach to explain how individuals respond to fear-inducing messages. The EPPM has been used extensively in health promotion campaigns which aim to encourage people to adopt healthy behaviours, including dental preventive care (e.g. Askelson, et al, 2014).

The EPPM model is based on the concept of "fight or flight." A person is likely to "flee" if the threat is great and there is little hope for the person to overcome the obstacle. The "flight" response is in reply to the fear a person feels. A person will more likely "fight" if the person believes the challenge is important enough and the person has the ability to win. EPPM purports that when someone is faced with a health problem, such as tooth decay, he or she may: a) sense no threat and do nothing; b) become fearful and ignore the health problem; or c) begin a danger control process that allows them to accept the challenge and take action.

According to the EPPM, perceived threat has two components: perceived threat susceptibility and perceived threat severity. The EPPM also incorporates both response

efficacy and self-efficacy. Self-efficacy refers to individuals' subjective beliefs that they can complete behavioural changes (Bandura, 2000). Response efficacy relates to the person's belief about how effective the recommended behavioural change will be to reduce the threat. If low, self-efficacy and/or response-efficacy reduce the likelihood that individuals will decide to change behaviour.

## Figure 2: Extended Parallel Process Model

If the perceived threat is low, the message will be ignored, efficacy will not be considered and no further action will be taken. However if the perceived threat is high the individual will follow one of two pathways, 'danger control processes or fear control processes' (Witte et al., 2001). If perceived threat and efficacy are both high the individual will follow the danger control pathway and focus on dealing with and solving the problems posed by the threat (Gore, 2005). If perceived threat is high but efficacy is low the individual will follow the fear control pathway. This involved maladaptive coping strategies such as denial, reactance or avoidance (Witte, 1992; 1994; Gore, 2005)

b) Risk (threat) perception:

From the qualitative study, we identified 5 perceived possible negative outcomes of poor oral health likely to be important to participants.

1=If your teeth were to make you feel uncomfortable when smiling, talking and laughing in front of people

2=If people thought you had failed to look after your own teeth

3=If your teeth were to become more painful and sensitive

4=If you were to need treatment which meant spending more time at the dentist

5=If you were to need treatment which you could not afford

Threat suceptibility: To eliminate the confounding effects of intentions to improve behaviour in future, participants will be asked to make conditional estimates of likelihood, "If you do not

follow the dentist's advice, how likely is it that.. [negative outcome..] Estimates are rated on a five-point Likert scale ranging from 1=absolutely unlikely to 5 absolutely likely.

Threat severity: Potential outcome severity is assessed using the question '*How serious* would it be to you if [negative outcome] were to occur, on a five-point Likert scale ranging from 1=not at all serious to 5=absolutely serious.

Self efficacy: will be assessed using a stem question of '*Please consider how confident you are that you can perform the behaviour properly, regularly and on a long term basis*' for each of the 6 target behaviours, using a 5 point Likert response scale from 1=not at all confident to 5=absolutely confident.

Response efficacy: will be assessed using the item format '{target behaviour] *means I am less likely to have dental problems,* using a 5 point Likert response scale from 1=Absolutely disagree to 5=Absolutely agree.

Affect regarding threat: To capture this we will ask participants how they would feel if they experienced each negative outcome (Brown, et al., 2013). and how vulnerable they feel to each negative outcome (Weinstein, et al., 2007). Again, five-point scales ranging from 1='not bad' at all to 5='absolutely bad' will be used.

Message Fear: Message fear will be assessed using the item format, '*how much did the advice you received make you feel... frightened/tense/nervous/anxious/uncomfortable*' using a five point Likert scale anchored with the statements 'not at all' and 'very much'

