credit-card sized information showing their risk level according to colour on the card. In the Verbal only arm patients will receive a plain card with a checklist where the message given by the dentist is written. The reverse of the credit-card sized information from the QLF arm and the Traffic Light arms will have the same checklist (Figure 1):

Figure 1: Checklist of possible preventive messages given to patients

- Stopping or quitting smoking
- Following your dental treatment plan

Following the check-up the dentist or nurse will record as data variables:

- The number of natural teeth present
- Whether the patient is exempt or not from NHS charges
- Any messages given as checked against the Figure 1 list
- The Red, Amber or Green risk rating assigned to patients in the Traffic Light arm

Following the dental appointment, all patients will be given the opportunity to revise their WTP for the information form experienced (therefore this will not be relevant to those in Model 1 who receive only verbal information and they will not undertake this part of the study). For this re-valuation, patients will be reminded of their initial valuation and then asked in a single open-ended question format if they wish to change the value and what amount they would change to.

Self-report data will then be collected at this point on:

- Intention to behave according to the behaviours listed in Figure 1 before the next appointment
- Behaviour change variables as outlined by the Extended Parallel Process Model (EPPM) (Severity of Threat, Susceptibility of Threat, Self-Efficacy and Response Efficacy). The 'threat' here will be the threat of poor oral health and its consequences identified from Phase 1 (for detail see Measures: 5b Risk (threat) perception). An additional set of items will be added to reflect affect concerned with negative oral health outcomes i.e. '*How would you feel if...*' (in addition to the cognition set reflected in EPPM domains).
- Patient-Clinician communication (Communication Assessment Tool, CAT).

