## Behaviour change and mediating variables

Plaque coverage provides an objective measure of tooth cleaning behaviour in the 48 hours preceding the measurement (because QLF images capture the maturity of the plaque), although it is not known whether consistent toothbrushing can be inferred. Plaque scores derived from the QLF analysis will be compared to the self-reported toothcleaning behaviour to assess the correlation between the two methods.

Differential reported behaviour change between the conditions will be assessed by creating a change score from one observation to the next by subtracting baseline scores from followup scores and conducting an analysis of mean differences using the baseline score as a covariate (Weinstein, 2007). Unless abnormally distributed, tooth cleaning behaviour will be treated as a continuum. Predicting oral health behaviours will involve the use of EPPM variables assessed during V1, and partly at V2 to predict later behavioural change.

The intervention is performed at the first visit. Thus, the change in EPPM scores (susceptibility to risk) from V1 to V2 will be used as the primary predictor variable. This will be used to predict changes in oral health behaviour from V2 to V3. We shall also use V1-V2 change scores to predict oral health behaviour changes from V2 to 6-month and 12-month (telephone) follow-ups. Structural equation models will be developed to represent these predictions, testing the predicted model as the model of best fit. Full information maximum likelihood methods (FIML) will be used to account for missing data (Muthén & Muthén, 1998–2010). With sample sizes greater than 250 participants, TLI, RMSEA, and SRMR are recommended. A TLI of .95, RMSEA of .06, and SRMR of .09 are recommended as cutoff values to accept the model as a good fit (Hu & Bentler, 1999).

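### The felt-vulnerability question shares the badness anchors of the anticipated-feeling question, so its answers could not be read as a vulnerability score

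*Protocol*

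**What the plan says.** The Measures section, item 5b, describes affect about the threat with two questions. The first is to "ask participants how they would feel if they experienced each negative outcome". The second is "how vulnerable they feel to each negative outcome". The sentence that follows gives the only anchors: "Again, five-point scales ranging from 1='not bad' at all to 5='absolutely bad' will be used".

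The Visit 1 procedure introduces the same material more briefly: "An additional set of items will be added to reflect affect concerned with negative oral health outcomes". The only stem it illustrates is the anticipated-feeling one. Vulnerability is not mentioned there.

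Item 5a gives the reason for including emotional measures, reporting that "measures that access these emotions often provide better prediction of behaviour than likelihood and severity ratings of risk". In the Phase 2 Analysis, under Behaviour change and mediating variables, "the change in EPPM scores (susceptibility to risk) from V1 to V2 will be used as the primary predictor variable".

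**The concern.** How bad an outcome would feel and how exposed a person feels to it are different quantities. Someone may dread unaffordable treatment and feel in no danger of it; someone else may dread it equally and expect it. A scale from not bad to absolutely bad has a place for the dread but no labelled place for the exposure. A participant asked about vulnerability has to guess what the numbers mean, and the analyst cannot tell how each participant guessed.

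What is at stake is one of the mediators collected at Visit 1. Response anchors are fixed when the answers are given, so no later analysis plan could recover a vulnerability score from answers on the wrong scale. That makes this an error in the protocol's wording rather than detail that may properly wait for an analysis plan.

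**Working it through.** No power, effect size or sample size enters, and the protocol states no figure to reproduce. The check sets each question in item 5b beside its anchors.

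| Measure | What is asked | Anchors | Fit |
|---|---|---|---|
| Threat susceptibility | likelihood, if advice is not followed | "Estimates are rated on a five-point Likert scale ranging from 1=absolutely unlikely to 5 absolutely likely" | yes |
| Threat severity | seriousness | "on a five-point Likert scale ranging from 1=not at all serious to 5=absolutely serious" | yes |
| Self-efficacy | confidence | confidence, low to high | yes |
| Response efficacy | agreement with a statement | disagree to agree | yes |
| Affect, first question | anticipated feeling | badness | yes |
| Affect, second question | felt vulnerability | badness | **no** |
| Message fear | how much the advice caused each emotion | not at all to very much | yes |
| Fear control responses | agreement with statements | disagree to agree | yes |
| Danger control response | likelihood of acting | unlikely to likely | yes |

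Three further steps:

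1. **Is a vulnerability scale given elsewhere?** No. Neither the Visit 1 procedure nor the rest of the Measures section supplies one.

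2. **Does another item stand in for it?** Not directly. Susceptibility is a likelihood judgement, conditional on ignoring the dentist's advice. The vulnerability question as worded carries no such condition and concerns a feeling.

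3. **How many items?** The protocol lists 5 negative outcomes and puts both affect questions to each. Assuming one item per question per outcome, there are 5 × 2 = 10 affect items, of which 5 × 1 = 5 concern vulnerability. The protocol does not state this count. If the set given at Visit 1 contains only the stem named in that procedure, the number of vulnerability items is 0. The range is therefore 0 to 5.

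Tracing the measure forward, Visit 2 repeats only the perceived-susceptibility items, and the primary predictor is the change in those. Felt vulnerability is not named in the analysis. It could enter only under the general intention to use Visit 1 variables from the behaviour-change model to predict later behaviour.

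**The case against.** The strongest reply is that this is a summary sentence that lost a phrase. It refers to scales in the plural, the questionnaire is not shown, and the questionnaire may carry sensible vulnerability anchors. Alternatively, the vulnerability clause may not describe a separate item set at all, which would agree with the Visit 1 procedure. Either may be true, but the text supports neither over the literal reading, and under both the protocol still needs correcting.

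The reply does defeat several stronger readings that a reader might infer:

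- *That the vulnerability items simply repeat how bad the outcome would be.* This is a plausible guess about behaviour. On a numbered low-to-high scale, some participants might still answer by degree of vulnerability. The documents show that the score is uninterpretable, not that it duplicates another.
- *That half of the affect items are invalid.* This assumes ten administered items, a number the protocol does not give.
- *That the plan can no longer test whether felt risk predicts better than rated risk.* The protocol cites that claim as a reason for choosing its model. No objective or analysis sets out to test it. Anticipated affect and message fear also remain measured, each on fitting anchors.
- *That the primary predictor is damaged.* Susceptibility is a separate measure with its own matched anchors.

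**Conclusion.** The point holds in limited form. Item 5b attaches badness anchors to a vulnerability question and provides no others, so the answers as specified could not be read as a vulnerability score and may overlap with anticipated affect and severity. The reach is one secondary mediator at Visit 1, with at most five items on the assumption of one per listed outcome. Susceptibility, anticipated affect, message fear, willingness to pay, the clinical outcomes and the sample size are untouched. The conclusion rests on the protocol text alone; sight of the questionnaire could show the error to be confined to the protocol's wording. This is a minor correction, worth making because it is cheap beforehand and cannot be undone once participants have answered.

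**What to change.** In the paragraph on affect regarding threat:

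- Restrict the badness anchors to the anticipated-feeling items.
- Give the vulnerability items their own five-point scale, 1 = not at all vulnerable to 5 = absolutely vulnerable, in the style of the neighbouring scales.
- State that the two are kept as separate scores.

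Then reconcile the Visit 1 procedure with the Measures section, so that both say whether the vulnerability items are asked at Visit 1.

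The cost is a line or two of text if the items are already in the questionnaire. If they are not, asking them adds up to five short items at Visit 1. No design, sample size or primary analysis changes.
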